The Judith Jaffe Multiple Sclerosis Center currently has over 1000 patients in a clinical and MRI database. Patients who have signed consent for the database will have their standard of care MRI scans monitored for new enhancing lesions; this will only have to be repeated if initial scan is not completed at our MS center with our current clinical protocol. All RRMS patients with new enhancing lesions will be considered for the study and approached regarding participation. Patients that are considered candidates and consent for the study, patients will then be randomized (1:1) to receive one course of ACTH followed by monthly pulses vs. receiving only one course of ACTH treatment. All patients will have follow-up MRI's at 3 months, 6 months and 12 months post lesion onset for a total of 3 additional scans. If a patient is identified as having an enhancing lesion from MRI scan not obtained through our database, an additional scan will be obtained through the study and serve as the baseline MRI. All patients will receive the first course of ACTH within 4 weeks of new lesion detection.

3.2: Study endpoints

The primary endpoint of this study will be change in MWF within new enhancing lesions over the course of 12 months. The absolute change in lesion MWF (over our test-retest variability) between baseline and one year MRI's will be calculated and compared between treatment groups.

The main secondary end-point will be longitudinal assessment of MWF (every 3 months) to determine the dynamics of myelin change over 12 months, specifically to determine the timing of remyelination. The advantage of T2 relaxometry is the ability to look at both the contribution of water within myelin bilayers (MWF) but also the water within the intra/extracellular compartment (the intermediate peak within the T2 spectrum). This second peak (extracellular peak) can increase with edema, thus once the extracellular pool stabilizes, we can ensure that any change in myelin water fraction (MWF) is a true reflection of myelination.

We will also explore a measurement called “absolute myelin content”. Through this measurement, we can control for the increased edema associated with a new lesion, thus providing for a more accurate measure of true myelin change.

Additional secondary end points include measurement of the following clinical measurements: EDSS, and the following MRI measurements: change in T2 lesion volume, whole brain volume, and cortical volume.

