If patients in either arm have an additional relapse during the study, they will be removed from the study. At that point patients are likely to change on-going treatment for their MS and based upon their treating physician, may require additional steroids (either ACTH or methylprednisolone)

3.3 Inclusion and Exclusion Criteria:

Inclusion criteria:

Patients with RRMS or SPMS with new contrast-enhancing lesions who will start as part of their standard of care ACTH.

Exclusion criteria:

- Patients having received oral or IV corticosteroids within one month prior to initial scan demonstrating contrast enhancing lesion
- Patients with known or new allergy to ACTH
- Patients being treated with Natalizumab, Rituximab, and Cyclophosphamide
- Patients unwilling to have serial MRI exams
- Patients unable to undergo MRI imaging because of having an artificial heart valve, metal plate, pin, or other metallic objects in their body or is unable to complete all the MRI scans required for this study
- Patients with acute or chronic renal disease in whom administration of gadolinium may pose risk of nephrogenic systemic fibrosis
- Patients that are pregnant
- Premenopausal woman not willing to use at least one form of contraception
- Patients with a known history of diabetes mellitus
- Progressive neurological disorder other than RRMS or SPMS
- Clinically significant cardiovascular disease, including myocardial infarct within last 6 months, unstable ischemic heart disease, congestive heart failure, or angina
- Subjects on chronic steroid therapy for treatment of MS or other systematic disease
- Subject currently has a significant medical condition (other than MS) including the following: neurological, psychiatric, metabolic, hepatic, renal, hematological, pulmonary, cardiovascular (including uncontrolled hypertension), gastrointestinal, urological disorder, or central nervous system (CNS) infection that would pose a risk to the subject if they were to participate in the study or that might confound the results of the study
 - Note: Active medical conditions that are minor or well-controlled are not exclusionary if, in the judgment of the Primary Investigator, they do not affect risk or the subject or the study results.

- Subject is unable to cooperate with any study procedures, unlikely to adhere to the study procedures and keep appointments, in the opinion of the Investigator, or was planning to relocate during the study

3.4 Randomization procedure:

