Given this is a small pilot study and a chance that simple randomization would course all patients to fall within one treatment group we will randomize patients *in permuted blocks*. This randomization scheme consists of a sequence of blocks such that each block contains a pre-specified number of treatment assignments in random order. The purpose of this is so that the randomization scheme is balanced at the completion of each block. Patients will be randomized after the consent is signed.

3.5 Sample Size:

We are proposing a pilot to study fifteen patients per study arm (for a total of 30 patients, includint ~ 10 screen failures) with new enhancing lesions over a 12 month time period. The longitudinal dynamics of MWF have only been studied in a handful of patients and the effect of any specific steroid treatment has not been studied, thus we are unable to propose a proper calculated sample size. However, from our preliminary longitudinal MWF lesion data, we are able to determine that at least 50% of new enhancing lesions show some signs of remyelination after initial acute treatment (methylprednisolone or ACTH). If we were to perform a sample size based upon an assumption that repeated course of ACTH will show a 25% greater proportion of lesions showing signs of improvement, we would require approximately 53 lesions per arm. In order to achieve that goal, we would have to screen and enroll at least 50 patients per arm. Therefore we are proposing a small pilot study to gain more information regarding the potential benefit of repeated courses of ACTH to allow for a more accurate design of a larger clinical trial. In addition, we will focus our efforts toward patients with more than one lesion in an attempt to reach a goal of at least 25 lesions per arm. We expect that repeated course of ACTH may profoundly affect the remyelination and hope to a much higher proportion of lesions showing repair. Again, we are hopeful that information gained from this pilot study can help to accurately calculate sample sizes for larger clinical trials as well as gain insight into the potential benefit of ACTH on remyelination.

3.6 Clinical visit schedule:

Screening visits: Patients will be screened during standard of care clinical visits for multiple sclerosis. If a patient had MRI within 2 weeks of visit and had new enhancing lesions, the patient will be asked to participate in the study.

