Baseline visit: Baseline EDSS (if not obtained during screening visit), *consent signed*, schedule repeat MRI with and without contrast if screening MRI not completed as part of the Weill Cornell Multiple Sclerosis Center Clinical Protocol. Initiation of ACTH (H.P. Acthar®) course of therapy following visit (patient will do home therapy) after randomization.

Visit 1: EDSS, safety evaluations, and initiation of monthly course of ACTH (H.P. Acthar®) in patients randomized to this arm.

Visit 2: EDSS, safety evaluations.

Visits 3, 4, 5: EDSS, safety evaluations, MRI with and without contrast

Visit 6 (last visit): EDSS, safety evaluations, MRI with and without contrast.

3.7 Study schema:

Tests and Evaluations	Time point: screening/ Baseline	Visit 1 (1 month)	Visit 2 (2 months)	Visit 3 (3 months)	Visit 4 (6 months)	Visit 5 (9 months)	Visit 6 (12 months- end of study)
Consent obtained	X						
MS history and EDSS, safety evaluations	X	X	X	X	X	X	X
Randomization to treatment arm	X						
MRI	X			X	X	X	X

4 Assessment and documentation of adverse events

An AE is any physical or clinical worsening in symptoms or disease experienced by the patient at any time during the course of the study, whether or not it is considered related to study participation

or procedures. Multiple sclerosis symptoms that worsen during the course of the trial will be treated as AEs. AEs may also include complications that occur as a result of protocol-mandated procedures.

ACTH Safety Background

ACTH has been approved by the US Food and Drug Administration for treatment of MS relapses, however, we are proposing to use this drug on a monthly pulsed dosing (80mg for three days per month) schedule for one year. A few trials have evaluated the longer-term clinical benefit and safety profile of ACTH pulse therapy in idiopathic glomerular diseases, such as nephrotic syndrome and focal segmental glomerulosclerosis (FSGS), as well as one pilot study in MS. These studies had varying dosing schedules, some of which included a higher per month drug exposure as compared to our proposed study [26-30]. None of the studies reported severe-events related to ACTH and the adverse events were consistent with the expected common side effect profile listed on approved label. Based upon these studies, the adverse events between the two groups of patients proposed in this study should be similar.

The studies are summarized below.

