- In an investigation of twenty-four patients with nephrotic syndrome from idiopathic FSGS, patients were treated with a median dose of 80 units injected subcutaneously twice weekly for up to 24 weeks [26]. ACTH gel provided a favorable safety profile with adverse events reported in 21 of 24 patients, most of which were mild and transient [26]. There were 52 typical steroid-related events (ranging from weight gain, mild elevation of BP, mood alteration) and no serious infections.
- In an investigation of 15 subjects with resistant glomerular diseases treated with 80 units of subcutaneous ACTH twice weekly for 6 months, no moderate to serious events or significant infections were reported with three of the 15 subjects reporting typical steroid-like adverse events (worsening glycemic control, weight gain, insomnia, mild elevation of BP and mild skin pigmentation changes) [28]. Importantly, no severe infections were reported.
- An investigation of twenty-one patients with nephrotic syndrome treated with ACTH gel twice weekly for up to 12 months reported five patients with steroid-like adverse events (impaired blood glucose control, weight gain, and 1 patient showed evidence of accelerated bone loss on bone densitometry not observed prior to ACTH gel therapy) but no severe infections [27].
- In a study of 23 nephrotic patients treated with an average of 25mg/week for a range of 5-11 months reported only similar steroid-related adverse events, all of which were mild [29].

In a pilot study in multiple sclerosis, monthly ACTH was compared to monthly IV methylprednisolone (corticosteroid). Twelve subjects tolerated a regimen of 80 units of ACTH injected subcutaneously for three consecutive days once a month for 12 month [30]. The ACTH pulse therapy proved to have a favorable relapse and psychiatric side effect profile when compared to IV methylprednisolone as well as a lower number of adverse events. The study reported no

moderate to severe events. Psychiatric episodes only occurred in the IV methylprednisolone group and the ACTH group had a significantly stronger improvement in Mental Health Inventory. The ACTH treatment group had a lower number of infection incidence rate. When the two treatment groups were compared, they reported a similar amount of disease-related significant adverse events.

Adverse events

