Use of H.P. Acthar Gel may be associated with central nervous system effects ranging from euphoria, insomnia, irritability, mood swings, personality changed, severe depression and psychosis. Existing emotional instability or psychotic tendencies may be aggravated.

Patients with a comorbid disease may have that disease worsened. Symptoms of diabetes and myasthenia gravis may be worsened with treatment.

Prolonged use of H.P. Acthar Gel may produce posterior subcapsular cataracts, glaucoma with possible damage to the optic nerves and may enhance the establishment of secondary ocular infections due to fungi and viruses.

H.P. Acthar Gel is immunogenic. Prolonged administration of H.P. Acthar Gel may increase the risk of hypersensitivity reactions. Neutralizing antibodies with chronic administration may lead to a loss of endogenous ACTH activity.

There is an enhanced effect in patients with hypothyroidism and in those with cirrhosis of the liver.

Decrease in bone formation and an increase in bone resorption both through an effect on calcium regulation and inhibition of osteoblast function may occur. These, together with a decrease in the protein matrix of the bone (secondary to an increase in protein catabolism) and reduced sex hormone production, may lead to the development of osteoporosis. Bone density should be monitored in patients on long term therapy.

H.P. Acthar Gel has been shown to have an embryocidal effect. Women of child-bearing potential should use approved methods of birth-control while administering the drug.

3. Adverse Reactions after Additional Postmarketing Experience

A. The following adverse reactions associated with the use of H.P. Acthar Gel have been identified from the postmarketing experience with H.P. Acthar Gel.

Allergic responses have presented as dizziness, nausea and shock.

Necrotizing angitis and congestive heart failure.

Skin thinning, facial erythema and increased sweating.

Pancreatitis, abdominal distention and ulcerative esophagitis.

Headache, vertigo, subdural hematoma, intracranial hemorrhage.

The adverse event collection period for this study begins at the baseline visit and will end after the last day of study medication. Patients discontinued from the study will be followed for at least 14 days after the last day of the study medication. At each visit patients will be specifically asked for adverse events using the table below.

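### Patients who relapse leave the study, not just study treatment, so their 12-month MRI for the primary endpoint is never taken

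*Protocol*

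**What the plan says.** The last paragraph of protocol section 3.2 reads: "If patients in either arm have an additional relapse during the study, they will be removed from the study". Its reason is that "At that point patients are likely to change on-going treatment for their MS" and that further steroids may be needed.

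The same section defines the primary endpoint: the absolute change in lesion MWF "between baseline and one year MRI's will be calculated and compared between treatment groups". Section 3.6 places the one-year scan at the end of the schedule: "Visit 6 (last visit): EDSS, safety evaluations, MRI with and without contrast". Neither section 3.6 nor the schema in section 3.7 lists an early-termination scan or any visit for patients who have been removed.

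The only follow-up stated for such patients is in section 4, within the adverse-event text: "Patients discontinued from the study will be followed for at least 14 days after the last day of the study medication". It names no MRI or EDSS. Section 3.5 sets the size ("We are proposing a pilot to study fifteen patients per study arm") and makes no allowance for removals.

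**The concern.** The rule merges two decisions: whether a relapsed patient continues study treatment, and whether that patient is still measured. A likely change of therapy is a good reason to mark or separate later scans. It is not a reason to stop taking them.

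Two things are at stake.

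- **Lost data.** Every relapse before month 12 removes a primary-endpoint value from a small pilot whose purpose is to inform a larger trial. The month-12 EDSS and brain-volume values go with it.
- **Possible bias.** Relapse occurs after randomisation. One arm receives monthly anti-inflammatory pulses and the other does not, so unequal relapse is plausible. The protocol's own evidence is indirect. In a small MS pilot cited in section 4, "The ACTH pulse therapy proved to have a favorable relapse and psychiatric side effect profile when compared to IV methylprednisolone", but that comparator was not a single ACTH course. If relapse differs by arm and is also related to how well the index lesions recover, the patients who still have a 12-month value are no longer comparable between arms.

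**Working it through.** **The plan's own figures.** The protocol gives no relapse rate, attrition rate or SD of MWF change, so there is no stated figure to reproduce on this point. The roughly 53 lesions per arm in section 3.5 is a separate illustration and is not used here. Rates and correlations below are assumptions, and effects are in SD units of MWF change.

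**Inputs from the protocol.** 15 patients per arm (3.5), 1:1 allocation (3.1), endpoint at month 12 (3.2), first follow-up MRI at month 3 (3.6, 3.7). Section 3.5 counts about 10 screen failures within the 30. If they are not replaced, about 10 per arm are randomised.

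**1. Data loss.** With relapse risk p in both arms, 15(1 − p) patients per arm remain. With one value per patient, the standard error (SE) of the arm difference is √(2/n).

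| p | Remaining of 15 | SE (SD units) | Rise over √(2/15) = 0.365 |
|---|---|---|---|
| 10% | 13.5 | 0.385 | 5% |
| 20% | 12 | 0.408 | 12% |
| 30% | 10.5 | 0.436 | 20% |
| 40% | 9 | 0.471 | 29% |

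Starting from 10 per arm, a 20% risk leaves 8.

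**2. Relapsers with no follow-up MWF.** With a constant hazard and yearly rate λ = −ln(1 − p), the share of relapsers who relapse before month 3 is (1 − e^(−λ/4)) / (1 − e^(−λ)).

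- p = 20%: 0.0543 / 0.20 = 27%, or 3 × 0.27 = 0.8 patients per arm.
- p = 40%: 0.1199 / 0.40 = 30%, or 6 × 0.30 = 1.8 patients per arm.

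**3. Bias of a completers-only comparison when treatment has no effect on MWF.** Let MWF change Y and relapse liability L be standard bivariate normal with correlation −r. A patient relapses if L > c, where P(L > c) = 1 − e^(−λ). Then E[Y | no relapse] = r·M(λ), with M = φ(c)/Φ(c).

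| λ per year | Risk | M | Completers of 15 |
|---|---|---|---|
| 0.25 | 22% | 0.381 | 11.7 |
| 0.5 | 39% | 0.634 | 9.1 |
| 1.0 | 63% | 1.024 | 5.5 |

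The bias in B − A (B = monthly pulses) is r·(M_B − M_A), and the SE is √(1/n_A + 1/n_B).

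| λ in A / B | r = 0.3 | r = 0.5 | SE | Largest bias/SE |
|---|---|---|---|---|
| equal | 0 | 0 | n/a | 0 |
| 0.5 / 0.25 | −0.076 | −0.126 | 0.442 | 0.29 |
| 1.0 / 0.5 | −0.117 | −0.195 | 0.540 | 0.36 |
| 0.25 / 0.5 | +0.076 | +0.126 | 0.442 | 0.29 |

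With r = 0 the bias is 0 at any rates. A simulation with 400,000 patients per arm agrees to within 0.005.

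A wider gap gives more. For risks of 40% (A) and 10% (B), M is 0.644 and 0.195, so the bias is −0.135 at r = 0.3 and −0.224 at r = 0.5. With 9 and 13.5 completers the SE is √(1/9 + 1/13.5) = 0.430, and 0.224/0.430 = 0.52.

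In this model the bias runs against the arm with fewer relapses, because that arm keeps more of the patients prone to poor recovery.

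**The case against.** The rule has a reason. Section 1.2 says that corticosteroids impair and delay remyelination in animal models, so rescue steroids or a new therapy could act on the quantity being measured. A mechanistic pilot may prefer the effect free of that. This stands as an argument for a pre-relapse analysis. It does not support ceasing to scan: with the later scans taken, both analyses are possible, and without them only one is.

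The bias is conditional and modest. The documents establish neither a difference in relapse by arm nor a link to MWF recovery, and the −0.195 figure needs a 63% relapse risk in arm A. With both risks at or below 40% and a twofold difference in rate, the largest value is 0.126 SD. This stands, and data loss is the firmer part of the concern.

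The figures also assume a completers-only analysis, which the protocol does not prescribe. About 70% of relapsers would have at least one follow-up scan before removal, and section 1.2 expects remyelination to be most prominent early. A longitudinal model could therefore recover part of the information. That is fair, but such a model must assume what happens after the last scan and cannot check it.

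EDSS is taken at every visit, so only its later values are lost. The 14-day sentence in section 4 sets a minimum and does not forbid longer follow-up.

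**Conclusion.** The concern holds and should be fixed. Read as written, the protocol stops collecting its own primary endpoint in every patient who relapses. This is a data-collection rule, so an analysis plan not shown here cannot repair it.

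The loss of data follows from any relapse, with or without bias: 13.5 to 9 of 15 patients per arm remain at assumed risks of 10% to 40%, and the SE rises by 5% to 29%. Bias needs relapse to differ by arm and to be related to MWF change. Even with equal risks, the same type of patient must be lost from each arm for the bias to be zero. Under the assumptions shown, a twofold difference in rate with r = 0.3 to 0.5 gives 0.08 to 0.20 SD, or 0.2 to 0.4 of an SE. A 40% against 10% risk gives up to about half an SE. Neither its size nor its direction can be settled from the documents, and it is modest against sampling error in a trial this small.

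**What to change.** Separate leaving study treatment from leaving the study. Suggested text for section 3.2: *A patient who relapses remains in study follow-up for all remaining scheduled MRI, EDSS and safety visits to month 12. The relapse date and any added steroid or change of MS therapy are recorded.*

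Report the comparison of all randomised patients in their assigned arm together with an analysis restricted to pre-relapse scans, and prespecify which is primary. Clinical management and study treatment after relapse stay with the sponsor and the treating physician.

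Reword the discontinuation sentence in section 4 so that it fits with continued follow-up. An allowance for loss in section 3.5 would help but is optional.

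The cost is a few sentences and two recorded items. The visits and contrast MRIs are already scheduled, although relapsed patients must be willing to continue them. The downside is that some retained scans will follow added steroids or changed therapy and may dilute the contrast. Setting the all-randomised result beside the pre-relapse result helps to show this.

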ACTH effects on myelination in MS patients

[name]
Judith Jaffe Multiple Sclerosis Center,
Weill Cornell Medical College,
[name],
[name]

1 Hypotheses and Rationale for the Study:

1.1 Hypothesis/Hypotheses:

Patients identified as having new enhancing lesions and treated with a course of ACTH at the time of initial MRI and then subsequently treated with monthly pulse doses of 3 days of ACTH treatment over one year will have a greater degree of remyelination as measured by myelin water fraction (MWF) as compared to those patients treated with one course of ACTH.

1.2 Rationale for the study:

MS is a chronic inflammatory disease of central nervous system characterized by focal T cell and macrophage infiltrates associated with demyelination. The primary innate immune cells in MS consist of infiltrating macrophages/monocytes and resident microglia. Cells of the innate immune system are effector cells that function to cause central nervous system (CNS) injury both through direct effects on neighboring cells, such as oligodendrocytes, and through generation of soluble proinflammatory mediators that have distant effects on cells, such as neurons. The innate immune inflammatory is thus sufficient to explain focal injury and diffuse injury. In the majority of patients, MS begins as a relapsing-remitting course but eventually evolves to a state of progressive decline in disability. Focal inflammatory demyelinating lesions are the predominant pathological findings in the patients with relapsing disease whereas diffuse axonal injury with microglial activation has been found to be the hallmark of progressive disease [1]. Microglial activation itself occurs either as a response to CNS injury for example as in Wallerian degeneration, or in response to signals from other inflammatory cells including macrophages and lymphocytes.

High dose corticosteroids (methylprednisolone) have been a mainstay of treatment for MS relapses and have been shown to shorten the time to recovery from relapses, presumably at least in part due to their anti-inflammatory effects. However, despite their anti-inflammatory properties, corticosteroids have been shown to impair and delay remyelination in animal models of MS [2, 3] and there is little clinical evidence of a longer-term beneficial effect.

[figure not shown]

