Adrenocorticotropic hormone (ACTH) gel, a long-acting formulation of the full sequence ACTH that includes other pro-opiomelanocortin (POMC) peptides, is considered an alternative to corticosteroids in the treatment of relapses (currently FDA approved for this indication). ACTH gel exerts direct anti-inflammatory and immune-modulating effects within the CNS, specifically on infiltrating macrophages and resident microglia [4, 5] as well as protecting mature oligodendrocytes from inflammation-related damage and excitotoxicity [6]. These effects are mediated not only via induction of endogenous corticosteroid production but also via effects on melanocortin receptors [7].

Chronic dosing of corticosteroids, specifically high dose methylprednisolone, (doses varying from once monthly to multiple doses every couple months) have been studied and found to be well-tolerated, safe and of a benefit on clinical as well as on conventional MRI measures of disease activity [8-10]. The rationale for these studies was based upon a potential benefit of chronic anti-inflammatory treatment to promote repair and neuroprotection. Following this same rationale, however instead implementing ACTH based upon its effect on the melanocortin receptors, we propose to study the benefit of monthly pulses of ACTH in a cohort of MS patients. We are targeting patients with new enhancing lesions to determine if monthly exposure to ACTH will promote more robust endogenous remyelination in new lesions compared to a one-time treatment course. We hypothesize that continued exposure to the anti-inflammatory effects of ACTH on new lesions would be superior to promoting remyelination as compared to a one-time treatment course. Given that the majority of endogenous remyelination is felt to begin within months after lesion development [11] and likely to be most prominent in the few months following, a one year study is most likely sufficient to measure this process.

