The treatment decision will be made by the patient's MS treating physician as part of standard of care for MS patients having an acute exacerbation. After the patient's treating physician has recommended ACTH, the study will be offered to the patient and the consenting process will be initiated, as described in eIRB. If the patient agrees to participate and signs the consent and HIPAA forms, he/she will become a study subject and randomized to one of two treatment groups. The initial stage of the study is for all patients to receive the standard of care course of ACTH and depending on the randomization, a patient may or may not receive additional monthly doses of ACTH. If the patient does not enroll into the study, ACTH will be prescribed as standard of care. Participation in this study will be offered to every eligible patient. Every physician in Judith Jaffe MS Center is an investigator for this study and will be discussing the study with their eligible patients.

The initial course of ACTH (H.P. Acthar®) will be administered as recommended in the package insert, a subcutaneous daily dose of 80-120 units daily for 2-3 weeks. However, as recommended in the package insert, the dosage may be individualized according to the medical condition of each

patient. Therefore, the frequency and dose of the drug may be determined by considering the severity of the disease and the initial response of the patient. The typical dosing for an MS exacerbation is 80units/day for 3-5 days and it is expected that this will be the initial dosing for the majority of the patients.

MS patients enrolled in this study will be randomized into:

Group A: 80units/day ACTH for 3-5 days (The dose could be adjusted based on the individual needs of the patients up to 80-120 units daily for 2-3 weeks.)

Group B: 80units/day ACTH for 3-5 days (The dose could be adjusted based on the individual needs of the patients up to 80-120 units daily for 2-3 weeks.), followed by monthly 80 units/day ACTH for 3 days for 12 months of treatment.

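### The pre-scan washout in Section 3.3 names oral or IV corticosteroids but not ACTH, so as written it admits a patient recently treated with the study drug

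*Protocol*

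**What the plan says.** The criteria that bear on earlier treatment are all in Protocol Section 3.3.

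- The only exclusion with a time window is "Patients having received oral or IV corticosteroids within one month prior to initial scan demonstrating contrast enhancing lesion".
- A second steroid exclusion has no window and concerns continuing use: "Subjects on chronic steroid therapy for treatment of MS or other systematic disease".
- The only exclusion that names ACTH concerns allergy: "Patients with known or new allergy to ACTH".
- The inclusion criterion is "Patients with RRMS or SPMS with new contrast-enhancing lesions who will start as part of their standard of care ACTH".

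Section 3.1 gives the route and labelled dosing of the study drug: "a subcutaneous daily dose of 80-120 units daily for 2-3 weeks". Section 1.2 presents ACTH gel as a substitute for corticosteroids in relapse and says of its actions: "These effects are mediated not only via induction of endogenous corticosteroid production but also via effects on melanocortin receptors". The closing paragraph of Section 3.2, on patients who relapse during the study, counts both ACTH and methylprednisolone as steroids.

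Section 1.1 sets monthly pulses after an initial course against a control described by the words "as compared to those patients treated with one course of ACTH". Section 3.1 defines the control in the same way, as a single course only. Section 3.2 makes the primary endpoint the change in lesion MWF from the baseline scan to one year.

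**The concern.** A washout before the qualifying scan shows that the sponsor regards recent anti-inflammatory treatment as a problem for that scan. By the protocol's own account of the mechanism, that reasoning covers ACTH as well. The criterion names a drug class and two routes, and the study drug fits neither part. The protocol gives no reason for treating the two differently, so this looks like an oversight.

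Two things are at stake. The first is the baseline. The primary endpoint is a change score, and Section 1.2 says that MWF can rise with edema. A lesion scanned soon after an ACTH course may therefore start from a different value than an untreated one. The second is the description of the control arm. A Group A patient who had an earlier course in the preceding weeks has not had only one course in that period. Eligibility is fixed in the protocol, so a later analysis plan cannot keep such patients out before randomisation.

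**Working it through.** No figure in the plan depends on this point, so there is none to reproduce. The check is a reading of the criteria, followed by a look at what randomisation does to the exposure.

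**Step 1: does any criterion reach a recent single ACTH course?**

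| Protocol text | Reaches it? | Reason |
|---|---|---|
| Timed washout, 3.3 | No | Limited to corticosteroids given orally or IV; ACTH is subcutaneous (3.1) and is set apart from corticosteroids (1.2) |
| Chronic steroid exclusion, 3.3 | No | One recent course is not chronic therapy |
| ACTH allergy exclusion, 3.3 | No | Concerns hypersensitivity, not exposure |
| Inclusion criterion, 3.3 | No | Looks forward to the course about to start; does not ask about earlier ones |
| Reference to the first ACTH course, 3.1 | No | Describes on-study treatment and its timing after lesion detection |
| Grouping of ACTH with steroids, end of 3.2 | No | Looser usage, in a passage on relapse during the study; the exclusion does not use it |

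Take two patients who differ only in what they received two weeks before the scan. The one given oral or IV methylprednisolone is excluded. The one given subcutaneous ACTH is not.

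**Step 2: when does the exposure occur?** It comes before the qualifying scan. Under Sections 3.4 and 3.6, consent and randomisation follow that scan. The exposure is therefore a baseline characteristic, equally likely in either arm.

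**Step 3: what does it do to the contrast?**

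- Pre-exposed Group A patient: earlier course + study course.
- Pre-exposed Group B patient: earlier course + study course + monthly pulses.
- Difference: monthly pulses, the same as for patients without earlier ACTH.

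Section 3.5 illustrates a sample size from 50% of lesions improving and a gain of 25%, read here as 0.50 against 0.75. Suppose a share f of each arm is pre-exposed and the earlier course adds d to the improvement rate in both arms. The difference is then (0.75 + f·d) − (0.50 + f·d) = 0.25, which is unchanged. It shrinks only if the earlier course helps Group A and not Group B. For example, with f = 0.20 and d = 0.25 in Group A alone, the control rate is 0.50 + 0.20 × 0.25 = 0.55, and the difference is 0.75 − 0.55 = 0.20. Both values are assumptions, and the documents give no ground for helping one arm alone.

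**Step 4: what remains?** Chance imbalance does. Section 3.5 plans 15 patients per arm, 30 in all, and that total includes about 10 screen failures. If the failures come out of the 30, the arms hold about (30 − 10)/2 = 10 each. Assume, for illustration only, that exactly two pre-exposed patients are randomised. Ignoring the blocks, the chance that both land in the same arm is 14/29 = 48% with 15 per arm, or 9/19 = 47% with 10 per arm. Under permuted blocks it is 1/2 if the two fall in different blocks and lower if they share one. Randomisation in arms this small cannot be relied on to balance a rare baseline feature.

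**The case against.** The strongest objection concerns the claim that a reader might infer first: that the gap contaminates the control arm and pulls it toward the experimental exposure. The documents do not support that. The earlier course precedes randomisation and falls on both arms in expectation, and the monthly pulses still separate the arms. A smaller contrast would need a ceiling on the benefit in Group B, and the protocol gives no evidence of one. This part of the objection stands in full.

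A reader might also want to put a share of the control arm on the problem. That cannot be done. Section 3.1 shows that the centre prescribes ACTH for exacerbations. It does not show that anyone has a course, then a new enhancing lesion, and then a fresh recommendation for ACTH within about a month.

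Three further arguments carry some weight. Sections 1.2 and 3.2 propose the extracellular T2 peak and absolute myelin content to separate edema from myelin change. These would address a baseline shift due to edema, but not a direct effect on myelin. The wording about starting ACTH and about a first course sits awkwardly with a patient being re-treated, but it is not a bar. This is also a single centre whose physicians are all investigators, so they may apply the washout to ACTH in practice. That would be a sensible reading, but it is not what the criterion says.

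Finally, widening the exclusion to corticosteroids by every route would catch inhaled, nasal or topical use, for which no case has been made. That also stands, and the fix avoids it.

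**Conclusion.** The gap is real on the text: the only timed washout omits the study drug, and no other criterion supplies it. The consequences are limited. The gap does not systematically bias the between-arm comparison, and the documents do not support calling the control arm contaminated. For any such patient who is enrolled, it can add noise to the baseline lesion MWF. It allows chance imbalance in arms of at most 15, and it makes the single-course description untrue if that patient is in Group A.

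The size is unknown because the protocol gives no frequency of recent ACTH use. The calculation with two patients shows only how easily an imbalance could arise; it does not estimate how many such patients there would be. The conclusion rests on reading the exclusion as written. If the sponsor already means it to include ACTH, the point reduces to a clarification of wording. In either case it is a cheap improvement to the plan and not a threat to its validity.

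**What to change.** Reconcile the exclusion with the treatment contrast by adding ACTH to the existing criterion in Section 3.3, so that it covers oral or IV corticosteroids, or ACTH. Keep the one-month window and the anchor to the initial scan that the protocol already sets, and do not extend the criterion to other corticosteroid routes. With the MS history that Section 3.7 already schedules at baseline, record the date of any earlier ACTH course, so that remaining exposure can be described by arm.

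The cost is one line in the eligibility list by amendment and one extra item in the baseline history. The downside is that a few recently treated patients become ineligible, which matters somewhat in a pilot of this size. The protocol gives no figure for how many.
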